As seen in [Figure 1](#), we will randomize up to 400 participants to 3 conditions: a) a weight stability intervention (Group 1); b) a weight loss intervention (Group 2); and c) a minimal intervention condition (Group 3). All 3 conditions receive a highly efficacious smoking cessation program and 6 months of varenicline pharmacotherapy (ChantixTM). Those participants randomized to Group 1 & 2 will receive monthly booster weight management sessions, after completing the smoking cessation intervention.

Figure 1. Study Design

5. Study Project Procedures

Intervention Trial Screening and Baseline Procedures. Individuals who meet the phone screening eligibility criteria will be invited to schedule a remote Screening Visit (via phone) and the participant's e-signature will be obtained via DocuSign. If the self-reporting questionnaires cannot be done via phone they may be emailed or mailed (along with an addressed and stamped envelope) to the participant for completion. If the participant does not want to use DocuSign, the consent form may be mailed to prospective participants with a return envelope and staff will conduct the consent process over the phone prior to the participant signing the consent form and mailing it back. If consent is done in this way, staff will wait to complete the rest of the remote Screening Visit until receiving the signed consent form. If appropriate, a pregnancy test will be mailed to the participant along with instructions and staff will obtain their self-reported pregnancy test result via a follow-up call. If the participant is willing, they may email a picture of their test result. Participants will receive information regarding how to complete 3 behavioral run-in items, as an indicator of their motivation to participate in the trial over the next 12 months.

Behavioral run-in tasks include:

1. A daily diet and exercise journal (3 days)
2. Liking the study on Facebook (encouraged, but not required)
3. Obtaining physician permission to participate

Participants will complete another remote study visit ("Baseline") to evaluate behavioral run-in performance and determine randomization eligibility. A BodyTrace e-scale will be mailed to the participant and they will be asked to weigh to confirm eligibility. If participants meet eligibility requirements, they may begin the randomization process.

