Intervention Fidelity Monitoring. Our previous experience in weight management and smoking cessation research suggests that the following quality procedures will help ensure treatment fidelity: 1) detailed intervention protocol development; 2) careful interventionist training, certification, and periodic re-training; 3) randomly select 20% of intervention sessions to record and code to ensure protocol adherence and to provide corrective feedback; 4) documentation of all intervention contacts to monitor participant exposure to treatment; and 5) weekly study meetings to review overall adherence to structured protocols and prevent any drift between interventionists. These study meetings (attended by the supervising investigators and the behavioral interventionists) will also include problem solving related to challenging cases and refining skills.

Measurement. Data collection visits will be scheduled at baseline, randomization, and at 2 month (after the weight management component), at 4 month (after completion of the smoking cessation intervention), at 8 month (after completion of the varenicline pharmacotherapy), and at 12 month follow-up. Follow-up measures will be obtained by trained staff who are blinded to treatment assignment ([Table 1](#)). Participants who complete the 4 month, 8 month and 12 month visits will receive a financial incentive. Participants will be asked to weigh themselves on their BodyTrace e-scale. If they report point prevalence abstinence, a cotinine test will be mailed to the participant along with instructions for use and reporting of the results. For all visits, if completely phone-based visits are not possible, then the self-reporting questionnaires may be emailed or mailed (along with an addressed and stamped envelope) to the participants for completion and entered into the database by trained staff who are blinded to treatment assignment.

Table 1. Study Phases and Measurement (X=for all participants; 0=for Group 1 & 2 participants)

	Phone Screening	Screening	Baseline	Randomization	Weight Management Phase										Smoking Cessation Intervention + Varenicline Phase					Weight Booster Sessions + Varenicline Phase					Follow-up Phase		
					-2	-1	0	1	2	3	4	5	6	7	8	9	10	11	12	13	14	16	20	24	28	32	
Inclusion/Exclusion	X																										
Informed Consent	X																										
Demographics	X																										
Urine Pregnancy Test (self-reported result)	X																										

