Why Do You Smoke: We will utilize the “Why Do You Smoke?” questionnaires that was adapted for assessing smoking specific weight concern. The scale shows evidence of predictive validity. A score of 7 or below indicates a low level of weight concern, whereas a score of 22 or greater indicates a high level of smoking specific weight concern. Participants will complete this 18-item measure by indicating their degree of agreement on a 6-point scale.

Self-Efficacy: We are assessing general self-efficacy with the Self-Performance Survey short form. These 4 items are rated on a 5-point scale.

Treatment Preference: We are assessing participants' preference for each of the treatment conditions at baseline to explore whether match or mismatch to treatment preference influenced outcome.

Weight Concern: We will measure participants weight concerns related to smoking. The 6 items on this scale are scored on a 10-point scale.

Return to Smoking: The 11 item scale (63) will be used to assess the degree of weight loss that may precipitate a return to smoking. Participants are asked if they would return to smoking after a gain of less than 2 pounds, and each subsequent question adds 2 pounds until the participant is asked, "If after quitting smoking you gained 20 pounds or more, would you start smoking?" Those that indicate that they would return to smoking after any weight gain will be classified as "weight concerned."

Importance of Weight and Smoking Cessation: The extent to which participants prioritized weight control and smoking cessation will be measured using 2 items rated on 10-point scales.

Smoking Behaviors: We will assess nicotine dependence with the Fagerström Test for Nicotine Dependence (100) and smoking status (both point prevalence and prolonged abstinence). For those participants who report point prevalence abstinence, we will test cotinine levels. Cotinine, a direct metabolite of nicotine, will be measured using the iScreen® OFD Cotinine test. iScreen is a valid and reliable method for verifying smoking status, with a specificity of >99%, a sensitivity of 97.6%. We will consider participants with at least 30 ng/mL cotinine in their saliva to be smokers; this liberal definition will avoid false positives due to secondhand smoke.

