Efficacy of Two Novel Behavioral Post-cessation Weight Gain Interventions

NCT03156660

Document Uploaded 21APR2022

Document Created JAN2019

Statistical Analysis

All of the analyses will be performed with SAS/STATv14.1. Data will be examined for distributional normality and outliers prior to any analyses. Descriptive statistics will be generated for all variables of interest included in the analysis, overall and by treatment arm. Univariate comparisons will consist of χ^2 tests and ANOVA. We will use similar analytical methods to compare baseline characteristics between study completers and non-completers at 12 months. Based on these findings appropriate adjustments will be implemented in the regression models.

Consistent with previous studies, outcomes will be analyzed on an intention-to-treat basis, including available data from all randomized cases, regardless of treatment adherence and smoking status. Missing outcome data will be imputed using Markov Chain Monte Carlo model based approach by treatment arm. Monotone missing data pattern will be created by using all available measured outcome data points. This approach is most suitable for an arbitrary missing data mechanism.

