We hypothesize that participants randomized to the SMALL, LOSS, and BIBLIO conditions will have similar rates of smoking cessation at 12-month assessment. Given that the outcome is binary (i.e., prolonged abstinence; yes or no) and the treatment conditions are nominal, we will use categorical analytical methods. To test the differences in prolonged abstinence between the intervention arms, we will apply χ^2 test and then a multivariate logistic regression model, with BIBLIO selected as the referent group compared to the other conditions. We will estimate the relative odds of a treatment effect on prolonged abstinence while adjusting for baseline demographics, smoking history (e.g., onset of regular smoking, quit attempts, use of tobacco products), process measures and other potential confounders. As such, we can test the associations and estimate effects of additional variables, besides treatment effect.

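### Abstinence is verified by a mailed cotinine test that the participant uses and reports, with no described check of the reading and no cotinine condition in the SAP outcome; a cheap change would strengthen it

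*Protocol*

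**What the plan says.** The protocol's Smoking Behaviors entry (section 5, Study Measures) assesses both point prevalence and prolonged abstinence by self-report and adds a biochemical check: "For those participants who report point prevalence abstinence, we will test cotinine levels". It presents the test as a valid and reliable means of verifying smoking status, "with a specificity of >99%, a sensitivity of 97.6" per cent, and gives one classification rule: "We will consider participants with at least 30 ng/mL cotinine in their saliva to be smokers".

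The Measurement paragraph of section 5 says how the test is delivered: "a cotinine test will be mailed to the participant along with instructions for use and reporting of the results". It does not describe observed sampling, a photo, a staff reading or return of a sample to a laboratory. The mailed instructions are not reproduced. The same paragraph says that follow-up measures are obtained by blinded staff, and it ties payment to attendance: "Participants who complete the 4 month, 8 month and 12 month visits will receive a financial incentive".

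For the other mailed test, for pregnancy, the screening procedures take a self-reported result and add: "If the participant is willing, they may email a picture of their test result".

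The SAP describes the cessation analysis this way: "Given that the outcome is binary (i.e., prolonged abstinence; yes or no"). It does not mention cotinine. Its general rule for gaps is: "Missing outcome data will be imputed using Markov Chain Monte Carlo model based approach by treatment arm". It also brings smoking status into the weight model as a moderator or a confounder.

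**The concern.** A biochemical check is meant to be independent of the claim it tests. Here the person who made the claim also uses the test and reports its result. A smoker willing to claim abstinence may be willing to report a negative test, or not to report one. The quoted sensitivity describes what the assay does with a smoker's saliva. It does not describe how often a false claim is detected under this procedure.

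Two gaps add to this. Neither document says how a claim is classified when no result comes back. And the SAP does not say whether a cotinine result, once obtained, changes the prolonged-abstinence outcome.

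At stake is the SAP hypothesis that the three arms have similar cessation at 12 months. Misreporting at the same rate in every arm pulls the observed rates together, towards the hypothesised result. Misreporting that differs by arm could create a difference that is not real. Misclassified smoking status also enters the weight model as a covariate or moderator.

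**Working it through.** The documents contain no power or event figure for this outcome, so there is nothing of the plan's own to reproduce. The calculation shows how far the procedure could depart from the quoted assay performance.

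**Inputs from the documents**
- Sensitivity 97.6%; specificity above 99%, taken as 99% (protocol, Smoking Behaviors).
- Planned allocation 160:160:80 (protocol, section 5).

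**Assumptions (not in the documents)**
- t, the true abstinence rate: 20% to 40%.
- f, the share of continuing smokers who claim abstinence: 5% to 20%.
- h, the share of those false claimants who run the test properly and report the positive: 1, 0.5 or 0 for the rates below.

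**Step 1: effective sensitivity = 0.976 × h**

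| h | 1 | 0.75 | 0.5 | 0.25 | 0 |
|---|---|---|---|---|---|
| Effective sensitivity | 97.6% | 73.2% | 48.8% | 24.4% | 0% |

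**Step 2: verified rate = 0.99t + (1 − t) × f × (1 − 0.976h)**

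With t = 30% and f = 10%, claimed abstinence is 0.30 + 0.70 × 0.10 = 37.0%. The verified rate is:
- h = 1: 0.297 + 0.07 × 0.024 = 29.9%
- h = 0.5: 0.297 + 0.07 × 0.512 = 33.3%
- h = 0: 0.297 + 0.07 = 36.7%

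Over the whole range of t and f, the verified rate exceeds the true rate by:
- h = 1: at most 0.2 points (t = 20%, f = 20%: 0.198 + 0.16 × 0.024 = 20.2%)
- h = 0.5: 1.1 points (t = 40%, f = 5%: 41.1%) to 8.0 points (t = 20%, f = 20%: 28.0%)
- h = 0: 2.6 points (42.6% against 40%) to 15.8 points (35.8% against 20%)

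**Step 3: equal misreporting in two arms**

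Take true rates of 30% and 20%, so the true odds ratio is (0.30/0.70)/(0.20/0.80) = 1.71. With f = 10% in both arms:
- h = 0.5: 33.3% against 0.198 + 0.08 × 0.512 = 23.9%; odds ratio 1.59
- h = 0: 36.7% against 0.198 + 0.08 = 27.8%; odds ratio 1.51

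A real difference shrinks.

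**Step 4: misreporting that differs by arm**

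Take t = 30% in both arms, with f = 20% in one (n = 160) and 10% in the other (n = 80). The last column is the chance of p < 0.05 (two-sided test) in the direction of the bias; with no bias it would be 2.5%.

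| h | Verified rates | Spurious difference | Chance of p < 0.05 |
|---|---|---|---|
| 1 | 30.0% v 29.9% | 0.2 points | about 3% |
| 0.5 | 36.9% v 33.3% | 3.6 points | about 8% |
| 0 | 43.7% v 36.7% | 7.0 points | about 18% |

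**The case against.** The strongest reply is that much of the concern rests on silence. The reporting instructions are not reproduced and might already ask for a photo. Table 1 marks the pregnancy test and height as self-reported but does not mark salivary cotinine so. This stands: a reader might infer that results go unseen, and the documents do not say that. The request remains reasonable, because if a photo is already required, one sentence would settle the matter.

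A reader might also infer that only a reported positive can overturn a claim, so that an unreturned test leaves the self-report standing. The documents do not state this either. Under the SAP's general imputation rule, an unreturned test could equally be treated as missing. What stands is that neither treatment is specified.

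A third tempting reading is that the test cannot catch misreporting at all. That is true only at h = 0. Some false claimants may report a positive or be deterred by the test, and payment is for completing visits, not for abstinence.

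The case for misreporting that differs by arm is also limited. All arms receive the same cessation programme and varenicline, blinded staff obtain the follow-up measures, and the booster sessions end at week 32, well before the 12-month outcome. One can construct a spurious odds ratio of 1.26 to 1.56: assume 20% true abstinence, have 5-10% of smokers in one active arm claim falsely and report a negative, and allow no false claims in the bibliotherapy arm, giving 24-28% against 20%. The arithmetic is right but the scenario is one-sided. With h = 0.5 and half the false-claim rate in the bibliotherapy arm (and perfect specificity), the same calculation gives 22.0% v 21.0% and 24.1% v 22.0%, odds ratios of 1.06 and 1.12.

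Finally, the main outcome is weight from the e-scale, which this test does not measure, and self-testing at home is a practical choice for remote visits. Both points hold, and they limit the weight of this point.

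**Conclusion.** The point holds as a cheap improvement. Verification depends on the participant's own report of the test, no check of the reading and no rule for an unreturned test is described, and the SAP outcome carries no cotinine condition. The 97.6% should be read as an upper limit on detection of false claims.

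Under the assumed ranges for t and f, the overstatement of abstinence runs from nearly nothing to 15.8 points, depending almost entirely on how many false claimants report their positive; at one half it is about 1 to 8 points. The documents give no figure for any of the three assumed quantities, so the actual size is unknown. Equal misreporting favours the hypothesised similarity between arms. Unequal misreporting could produce a false difference of unknown size.

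A reader might go further and conclude that the trial will present unverified self-report as cotinine-verified abstinence. The documents do not support that, because nowhere do they say how the endpoint will be labelled. The effect is confined to the cessation outcome and to smoking status as a covariate or moderator in the weight model.

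**What to change.** **Protocol, section 5, Measurement.** Ask participants to email a dated photo of the test device, to be read by staff blinded to assignment. The protocol already accepts an optional photo for the pregnancy test, and eligibility already requires daily email access.

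**SAP, cessation outcome.** Define verified abstinence as self-reported prolonged abstinence plus a staff-read cotinine below 30 ng/mL at 12 months. Class a claim with no readable result as unverified, and say how this rule sits with the SAP's imputation of missing outcomes. Report the self-report-only rate beside the verified rate, by arm.

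**Cost.** Wording in two documents, an emailed image and staff time to read it; no new assay. Some true quitters who send no photo will count as unverified, so the verified rate will be somewhat lower; the self-report rate beside it bounds that loss. A photo does not prove whose saliva was tested, so it reduces misreporting but does not restore the full 97.6%. Video observation and a change to what triggers testing are not needed for this.

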Efficacy of Two Novel Behavioral Post-cessation Weight Gain Interventions

NCT03156660

Document Uploaded 21APR2022

Document Created 10NOV2020

1. Purpose

Although smoking cessation accrues significant health benefits, regardless of the duration of smoking (4, 25, 26), it is typically accompanied by weight gain. A recent meta-analysis quantified this weight gain as, on average, 1.1 kg, 2.3 kg, 2.9 kg, 4.2 kg, and 4.7 kg at 1, 2, 3, 6, and 12 months after quitting, respectively (9). Concerns about postcessation weight gain are common and are often cited as a reason to delay cessation attempts (10, 11); furthermore, postcessation weight gain is associated with smoking relapse (10-12).

While there is some ongoing debate (13-15) about the effectiveness of behavioral weight management programs in conjunction with smoking cessation programs, it appears that behavioral weight management programs have not been able to successfully reduce postcessation weight gain (16). In addition, contrary to popular belief, there was no indication that involvement in weight management programs impacted abstinence (16, 17). Moreover, while some short-term weight gain attenuation has been observed with some pharmacotherapies (e.g., nicotine replacement therapy, varenicline), there is no long-term weight gain prevention benefit for any of the pharmacotherapies (27-30).

Much like weight maintenance after weight loss has proven to be challenging (18), weight maintenance after smoking cessation has been difficult to achieve. In a trial unrelated to postcessation weight gain, Wing and colleagues (19) hypothesized that making small, consistent changes may be beneficial for weight gain prevention. Wing *et al.* (19) tested this hypothesis in a recent study and found that participants who received their 'Small Changes' intervention gained significantly less weight as compared to the control group. Given these positive results, this approach may be translated to interventions focusing on other individuals at high risk for weight gain (i.e., those who are about to undertake smoking cessation).

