- Participants must have a self-reported BMI of 22 kg/m² or greater, as it would not be recommended to have those who are underweight or the lower end of the normal BMI range attempt a 5% weight loss (if assigned to Group 2)
- Participants must have access to a telephone and daily access to email. If using a cell phone, participants must be willing to use their cell phone minutes for weekly phone interventions as well as for some or all of the remote data collection visits
- All women of childbearing age must have a negative pregnancy test and must agree to use contraception during participation in the study
- Participants must also be willing to be randomized to the study conditions and wait eight weeks prior to beginning smoking cessation (during which they will participate in the weight management intervention to which they are assigned)
- Participants must have blood pressure that is < 150/95 mmHg and heart rates of >40 beats per minute and <120 beats per minute (according to their health care provider)
- Participants must be able to exercise for at least 10 minutes
- Participants must also have the ability to understand the consent process in English

Exclusion Criteria:

[figure not shown]
- Have a known contraindication, allergy or hypersensitivity to Varenicline

- Are currently (in the previous 30 days) participating in other behavioral or pharmacologic weight or smoking cessation interventions
- Have used an investigational drug within the last 30 days
- Have current suicidal thoughts or have a lifetime history of a suicide attempt as defined by the Columbia-Suicide Severity Rating Scale (C-SSRS) (76)
- Have a self-reported history of psychosis, bipolar disorder or anorexia nervosa
- Self-report current alcohol abuse or illicit substance use
- Have kidney disease or liver disease; HIV; have unstable cardiovascular conditions, or have history of cancer in the last 5 years
- Taking medications that impact weight (see list)
- History of gastric bypass, stomach stapling, banding or other weight loss surgery
- Lost \geq 10 pounds in the last 6 months
- Have another member of their household already participating in this study
- Pregnancy within the last 6 months, breastfeeding or planning to become pregnant during the study follow-up time (12 months)
- Weight limit of 385 pounds

4. Research Design

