Smoking History	X																										
Why Do You Smoke	X																										
Self-Efficacy	X																										
Treatment Preference	X																										
Weight Concern	X																										
Return to Smoking	X																										
Importance of Weight and Smoking Cessation	X																										
Smoking Behaviors	X																									X	X
Difficulty of Weight Program and Perceived Effectiveness	X																										
Difficulty of Smoking Cessation Program																										X	X
Weight Efficacy Lifestyle	X																									X	X
Weight Management Behaviors																										X	X
Perceived Stress	X																									X	X
Healthy Days	X																									X	X
Physical Activity	X																									X	X
Depression	X																									X	X
Suicidality	X																									X	X
Height (self-reported)	X																										
Bodytrace Weight	X*	X	X	X	X	X	X	X	X	X	X	X	X	X	X	X	X	X	X	X	X	X	X	X	X		
Adverse Events		X	X																							X	X
Intervention Adherence					0	0	0	0	0	0	0	0	0	X	X	X	X	X	X	0	0	0	0	0			
Varenicline Adherence																										X	X
Salivary Cotinine																										X	X
Program Satisfaction																										X	X

*Self-reported weight rather than BodyTrace will be recorded at SV

Study Measures.

Demographics and Contact Information: Participants will complete a questionnaire regarding their gender, age, marital status, race, ethnicity, education level, income, as well as provide contact information to facilitate high retention rates, which will be updated at each data collection visit.

Smoking History: We will assess the age at which participants first started smoking cigarettes regularly, whether they have smoked at least 100 cigarettes in their life, how many years they have been a regular smoker, number of cigarettes per day smoked in the past year, number of quit attempts, and the length of the most recent quit attempt. We will also assess the frequency of use of various nicotine and tobacco containing products over the past year.

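### The 30 ng/mL cotinine rule records abstinent users of nicotine replacement as smokers, and no described follow-up question would identify them

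*Protocol*

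**What the plan says.** The rule is in Protocol section 5, Study Measures, Smoking Behaviors.

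- Who is tested: "For those participants who report point prevalence abstinence, we will test cotinine levels".
- What is measured: "Cotinine, a direct metabolite of nicotine, will be measured using the iScreen® OFD Cotinine test". The stated accuracy is a specificity above 99% and a sensitivity of 97.6%.
- How the result is read: "We will consider participants with at least 30 ng/mL cotinine in their saliva to be smokers". The reason given for the cut-off is that "this liberal definition will avoid false positives due to secondhand smoke".

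Use of other products is mentioned in two further places.

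- Smoking History, in the same section: "We will also assess the frequency of use of various nicotine and tobacco containing products over the past year". Table 1 gives that row a single mark, at entry.
- The exclusion criteria in section 3 rule out people who "Are currently (in the previous 30 days) participating in other behavioral or pharmacologic weight or smoking cessation interventions". This is a condition of entry with a 30-day look-back.

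At follow-up, Smoking Behaviors is described as the Fagerström test plus point prevalence and prolonged abstinence.

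The SAP's cessation outcome is prolonged abstinence at 12 months, as a yes/no variable. It lists tobacco product use as a smoking-history covariate and says nothing about how a positive cotinine result is handled. It also brings smoking status into the weight models, as an effect modifier or an adjustment variable.

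**The concern.** By the Protocol's own description, the marker shows exposure to nicotine, not to cigarettes. A higher cut-off can separate a smoker from someone breathing other people's smoke. It cannot separate a smoker from someone taking nicotine directly. A participant who has stopped smoking and uses a nicotine patch at the 12-month visit reports abstinence, tests positive and is recorded as a smoker.

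There is time for this to happen. The 8-month visit follows the end of study varenicline, so about four months (12 − 8) remain before the final visit, and no restriction on nicotine products is described for that period.

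Two quantities are at stake: the cotinine-verified point prevalence rate, and the smoking status that enters the weight models. The second matters because section 1 of the Protocol associates nicotine replacement with less short-term weight gain, so the people moved into the smoker group may differ in weight from those they join and those they leave.

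**Working it through.** The documents give no abstinence rate and no rate of product use, so there is no plan figure to reproduce. The check has two parts.

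**1. Does anything in the text close the gap?**

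- *Exception in the rule:* none. No second marker is named, and secondhand smoke is the only false-positive source considered.
- *Bar on products during the trial:* none found. The entry exclusion covers other cessation interventions in the previous 30 days. It does not reach past enrolment and does not name e-cigarettes or smokeless tobacco.
- *Question at follow-up:* none described. The product question belongs to Smoking History, which is marked once.
- *Rule in the SAP:* none. Product use appears only as a covariate.

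The data would therefore show who reported abstinence and tested positive, but not which of those people had another source of nicotine.

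**2. How large could it be? (illustration)**

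Inputs:

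- N = 400 (Protocol sections 3 to 5).
- Specificity 0.99 (Protocol states above 99%).
- p = true abstinence. **Assumed** 30%, range 20% to 40%.
- f = share of true abstainers at or above 30 ng/mL because of another nicotine product. **Assumed** 5%, 10% or 20%.

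Formulas:

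- Effective specificity among abstainers = 0.99 × (1 − f)
- Verified abstinence = p × 0.99 × (1 − f)
- Extra abstainers recorded as smokers = 400 × p × 0.99 × f

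At p = 30%:

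| f | Effective specificity | Verified abstinence | Extra misclassified |
|---|---|---|---|
| 0 | 99.0% | 29.7% | 0 |
| 5% | 94.1% | 28.2% | 400 × 0.30 × 0.99 × 0.05 = 5.9 |
| 10% | 89.1% | 26.7% | 11.9 |
| 20% | 79.2% | 23.8% | 23.8 |

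Over p = 20% to 40% the count runs from 400 × 0.20 × 0.99 × 0.05 = 4.0 to 400 × 0.40 × 0.99 × 0.20 = 31.7.

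**Effect on the arm comparison.** If f is the same in every arm, every rate is multiplied by the same factor. Arms with equal true abstinence stay equal, and the odds ratio stays 1.0. A spurious difference needs unequal f. With p = 30% and f of 5% in one arm and 15% in another, verified rates are 28.2% and 25.2%. The odds ratio is (0.252/0.748) ÷ (0.282/0.718) = 0.86, or 1.16 taken the other way round. With 0% and 20% the rates are 29.7% and 23.8%, odds ratio 0.74. These splits are hypothetical, and nothing in the documents says which arm would have more use.

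**The case against.** Several points on the other side stand and set the limits of this one.

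- **Link to the SAP outcome.** A reader might infer that the rule falsifies the trial's cessation outcome. The documents do not support that: cotinine is tied to reported point prevalence abstinence, and no text applies it to prolonged abstinence.
- **Who is affected.** The rule's wording could be read as covering all participants, but only those who report abstinence are tested.
- **Meaning of abstinence.** It is not defined by product. If it means all tobacco, smokeless users are classed correctly. If it means all nicotine, there is no misclassification from these products. The lack of a definition is itself part of the gap.
- **Bias between arms.** A reader might argue that Group 3, which has no booster sessions, would turn to nicotine products more often. The boosters deal with weight management and end at week 32, and all arms get the same cessation programme and varenicline. That gives no ground for expecting different use. Even the hypothetical odds ratio of 1.16 is small beside sampling error: with 160 v 80 participants the standard error of the log odds ratio is about 0.31, a 95% interval of roughly 0.63 to 2.14.
- **Weight.** The Protocol sentence that credits nicotine replacement with a short-term effect goes on to deny any long-term benefit. The SAP's intention-to-treat weight comparison includes participants whatever their smoking, so a contrast fitted without smoking status is untouched.
- **What is asked.** The questionnaires are not reproduced, so not asked means not described. A single mark in Table 1 is not conclusive either: Demographics also has one, although its contact details are updated at each visit. One entry in the exclusion list is also not legible in the public copy.
- **The present rule is conservative.** If self-report overrode a positive test, a relapsed smoker who also vapes would count as abstinent. This is a good reason not to replace the rule outright.

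None of these supplies a way to identify an abstinent nicotine replacement user at follow-up.

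**Conclusion.** The concern holds for a limited set of results. As written, the rule records abstinent users of nicotine replacement as smokers, unless abstinence is meant to include all nicotine. It does the same to e-cigarette and smokeless users if abstinence means from cigarettes. No described data item would allow this to be corrected later. Cotinine-verified point prevalence and any smoking status derived from it for the weight models are affected. Prolonged abstinence is affected only if the sponsor also verifies it by cotinine.

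The size cannot be derived from the documents. The figure of about 6 to 24 of 400 rests on assumed true abstinence of 30%, assumed product use of 5% to 20% among abstainers, and a specificity of 0.99. Misclassification of that kind lowers all rates. The documents do not support going further and calling the comparison between arms biased, because that needs use to differ by arm and they give no evidence that it does.

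**What to change.** 1. Add one item to Smoking Behaviors at the 4-, 8- and 12-month visits: use in the past 7 days of nicotine replacement, e-cigarettes, or other non-cigarette nicotine or tobacco.
2. State in the Protocol and SAP whether abstinence means from cigarettes, from all tobacco or from all nicotine, and whether cotinine verifies prolonged abstinence.
3. Flag participants who report abstinence, test at or above 30 ng/mL and report such use as not biochemically verifiable.
4. Report the abstinence analyses, and the weight analyses that use smoking status, both ways: flagged participants counted as smokers, and flagged participants classed by self-report.

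The cost is one questionnaire item, a few sentences of definition and a second run of the affected models. The small downside is that the self-report version rests on unverified abstinence for the flagged participants. Reporting both versions shows how much depends on that.
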